## 10.2 Follow-up Reporting by the Principal Investigator

The SAE eCRF completed initially must be updated by the Principal Investigator or delegate sub-Investigators within 24 hours after the awareness of any THL study personnel of any new relevant information concerning the SAE (eg, outcome, precise description of medical history, results of the investigation). All relevant information must be included directly in the SAE eCRF.

An e-mail alert will be sent automatically to the GPV Department, the CRA, and the CTL. Copies of documents (eg, medical records, discharge summary, autopsy) may be requested by the GPV Department.

The anonymity of the subject must always be respected when forwarding this information.

### **10.3 Reporting of SAEs Occurring After a Subject Has Completed the Study**

Not applicable.

### **10.4 Assessment of Causality**

The causal relationship between the SAE (ie, fatal SAE, AESI, or SAR) and the product administered will be evaluated by the Principal Investigator as described in [Section 9.2.2.3.3](#).

Following this, the Sponsor’s Global Safety Officer will also assess the causal relationship to the product, based on the available information and current medical knowledge.

The causal relationship to study procedures will also be assessed in the SAE eCRF.

The decision to modify or discontinue the study may be made after mutual agreement between the Sponsor and the Principal Investigator.

### **10.5 Reporting SAEs to Health Authorities and IECs**

The Sponsor will inform the relevant health authorities of all SARs, fatal SAEs, and AESIs (regardless of causality) according to local regulatory requirements. Non-fatal SAEs will be reported in the Development Safety Update Report (DSUR) to relevant health authorities.

The Sponsor’s RMO will notify the Principal Investigator in writing of the occurrence of any reportable SAEs. The Principal Investigator / Sponsor will be responsible for informing the IECs that reviewed the study protocol based on the national requirements.

### **10.6 Reporting of Cardiovascular and Respiratory Events**

Cardiovascular and respiratory effectiveness endpoints as specified in this protocol will not be considered as SAEs and are waived from regulatory reporting to health authorities except if the Principal Investigator according to his/her best medical judgment considers these events as endpoint-related SARs. In that case, the Principal Investigator or delegate sub-Investigators must report the endpoint-related SAR within 24 hours after the awareness of any THL study personnel to the Sponsor’s GPV Department, the CRA, and the CTL using an SAE eCRF in the EDC system. The Sponsor will inform the relevant health authorities of the endpoint-related SAR according to local regulatory requirements.

In addition, the Sponsor will provide summaries of endpoint-related SAR on a quarterly basis to the relevant health authorities.

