#### ***Serious Adverse Reaction (SAR) and suspected SAR:***

All noxious and unintended responses to the study vaccine related to any dose administered that results in death, is life-threatening, requires hospitalization or prolongation of existing

---

a The term "life-threatening" refers to an event in which the subject was at risk of death at the time of the event; it does not refer to an event which hypothetically might have caused death if it were more severe.

b All medical events leading to hospitalizations will be recorded and reported as SAEs, with the exception of: elective hospitalizations planned either before or after inclusion into the study or outpatient treatment with no hospitalization, or hospitalizations due to an AE defined in the primary endpoint.

c "Persistent or significant disability or incapacity" means that there is a substantial disruption of a person's ability to carry out normal life functions.

hospitalization, results in persistent or significant disability or incapacity, or is a congenital anomaly or birth defect.

A SAR refers to a potential causal relationship between the study vaccines and an SAE, based on the HCP assessment.

A suspected SAR refers to individual SAR cases reported by the HCPs where a causal relationship between the SAE and the study vaccines is suspected by either the Principal Investigator or the Sponsor.

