#### 9.2.2.3.2 Serious Adverse Events

Information on non-fatal SAEs will be collected from the health registers, from inclusion until 6 months after vaccination. Non-fatal SAEs will not be individually assessed for causality. Instead, they will be evaluated statistically by comparing the frequency of SAEs to a baseline incidence estimated from the same health registers.

Information on SARs (suspected to be related to the vaccine by the HCPs), fatal SAEs, and AESIs will be collected and assessed throughout the study. Every SAR must be reported, even if the Principal Investigator considers that it is not related to the vaccine.

Any SAR (suspected to be related to the vaccine by the HCPs), fatal SAE, or AESI occurring at any time during the study will be reported by the Principal Investigator using the SAE electronic case report form (SAE eCRF) in the electronic data capture (EDC) system according to the Completion Instructions provided by the Sponsor. All information concerning the SAE is to be reported either as part of the initial reporting or during follow-up reporting if relevant information became available later (eg, outcome, medical history, results of investigations, copy of hospitalization reports. See [Section 10](#) for further details on SAE reporting).

For each SAR/AESI, the following information is to be recorded:

- Diagnostic (SAR/AESI) or ICD-10 code (Fatal: non SAR/AESI)
- Start and stop dates
- Whether the SAE was related to the investigational product

The Principal Investigator will assess the causal relationship between the SARs (suspected to be related to the vaccine by the HCPs), fatal SAEs, and AESIs and the investigational product as either “Not related” or “Related”, as described in [Section 9.2.2.3.3](#).

- Action taken for each SAE (eg, medication)

The action(s) taken by the subject to treat and/or manage any SAEs will be classified in the SAE eCRF using the following list (all applicable items should be checked):

- None
- Medication
- Health care provider contact
- Hospitalized

For each SAR/AESI, the Principal Investigator or a delegate will complete all the following criteria: outcome, elapsed time, and relationship to study procedures.

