4.3.1.4 Nature of the eSAE

eSAE refers to at least one of the following classes: SAR, AESI or fatal. It's an extraction of pharmacovigilance database and keeping key variables.

In addition, potentially related SAE (eg, in paper form) by any HCP but assessed as unrelated by the investigator are presented. Therefore, such eSAE are considered as "Other eSAE" in the statistical analysis.

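### For a non-fatal endpoint hospitalization that an HCP suspects and the Principal Investigator does not, the protocol gives two incompatible SAR reporting rules

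*Protocol*

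**What the plan says.** The general rule is in Protocol 9.2.2.1, 9.2.2.3.2 and 10.1. The definition rests on the HCP's view: "A SAR refers to a potential causal relationship between the study vaccines and an SAE, based on the HCP assessment". Section 9.2.2.3.2, like the Synopsis, removes any investigator veto: "Every SAR must be reported, even if the Principal Investigator considers that it is not related to the vaccine". Section 10.1 makes receipt of an HCP's SAR/AESI paper form a trigger for the 24-hour SAE eCRF. It also obliges the investigator to document HCP-suspected SARs and notify the sponsor of them regardless of causality. Under 10.4, after the investigator's assessment, "the Sponsor’s Global Safety Officer will also assess the causal relationship to the product". Under 10.5 the sponsor informs health authorities of all SARs. None of these sections excepts cardiovascular or respiratory events.

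The special rule is Protocol 10.6. Endpoint events "will not be considered as SAEs and are waived from regulatory reporting to health authorities". The only way out of this waiver is stated as a condition on one person's opinion: "except if the Principal Investigator according to his/her best medical judgment considers these events as endpoint-related SARs". The reporting duty follows from that condition: "In that case, the Principal Investigator or delegate sub-Investigators must report the endpoint-related SAR within 24 hours". Two other places support the carve-out. Footnote b to the SAE definition in 9.2.2.1 excepts from SAE recording elective stays, outpatient treatment "or hospitalizations due to an AE defined in the primary endpoint". Section 10.1 leaves cardiovascular and respiratory hospitalizations out of the twice-monthly aggregate table of non-fatal SAEs.

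SAP 4.3.1.4 says that SAEs judged potentially related "by any HCP but assessed as unrelated by the investigator are presented", and classes them as Other eSAE. SAP 4.3.1.5 calls an eSAE a SAR only when the investigator's final assessment is related. SAP section 4 describes the eSAE panel as holding deaths, related SAEs and AESIs.

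**The concern.** The plan elsewhere takes care that one blinded assessor cannot remove an HCP's suspicion from the safety record. The case is entered, the investigator gives an opinion, and the sponsor gives a second one. Read literally, 10.6 withdraws that protection for one group of diagnoses and makes the investigator's view the condition for opening the case at all.

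The group is broad. The primary endpoint list includes I30, I31, I38-I42 and J40-J47, among other codes. Protocol 1.3.2.1 names dyspnea, wheezing, throat tightness and chest pain among events reported with the trivalent high-dose vaccine. The documents do not say under which codes a serious reaction of that kind would be filed, so the overlap is possible but not shown.

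At stake is the completeness of the SAR and eSAE tables, which serve a stated secondary objective, and of expedited reporting.

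**Working it through.** The plan gives no figure to reproduce, so the check is to follow one case through both sets of rules. The case is an unscheduled, non-fatal inpatient stay starting at least 14 days after vaccination, with a listed primary discharge code. An HCP sends in a SAR/AESI form, and the Principal Investigator considers the event unrelated.

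| Step | General rule | 10.6 with footnote b |
|---|---|---|
| Is it an SAE? | Yes, inpatient hospitalization (9.2.2.1) | No (10.6); excepted from SAE recording (footnote b) |
| Is it a SAR? | Yes, the HCP suspects it (9.2.2.1) | Only if the investigator considers it one |
| SAE eCRF within 24 hours? | Yes, on receipt of the form (10.1), despite the investigator's view (9.2.2.3.2) | The duty is stated only where the investigator considers it a SAR |
| Sponsor's causality opinion (10.4)? | Yes | No eCRF to act on |
| Health authorities? | Yes, all SARs (10.5) | Waived |
| SAP class | Other eSAE (4.3.1.4) | Absent unless an eCRF was opened |

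**Does either rule take priority?** No text says so. The general rule does not clearly win, because 9.2.2.1 defines a SAR as a causal link with an SAE, while 10.6 and footnote b say this event is not to be treated as one. A reader can therefore conclude that it is neither an SAE nor a SAR. Section 10.6 is also the more specific section, and staff could reasonably follow it. On the other side, 9.2.2.1 defines a suspected SAR as an HCP-reported case in which either the investigator or the sponsor suspects causality. The sponsor can hold that view alone only if rejected cases reach it.

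**What is kept if 10.6 is followed.** The stay is in the HILMO panel (SAP section 4), and arm is known after unblinding. The panel description gives no sign that it carries the HCP's suspicion. Deaths are collected irrespective of causality (SAP 3.2). The primary rVE analysis counts register hospitalizations and does not use the eSAE panel.

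**Scale.** SAP 5.5 gives about 450 primary-endpoint cases in the one season run. The documents give no rate of HCP suspicion or of investigator rejection. As an illustration only, assume that HCPs suspect the vaccine in 0.2% to 1% of cases:

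- suspected: 450 × 0.002 = 0.9 to 450 × 0.01 = 4.5;
- at risk of not being entered, if half are rejected: 0.45 to 2.25;
- at risk, if all are rejected: 0.9 to 4.5.

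These are upper values even on those assumptions. They suppose that 10.6 was always followed, and they include stays that ended in death.

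**Two related mismatches.** The protocol defines a SAR by HCP assessment, and SAP 4.3.1.5 by final investigator assessment. The panel description in SAP section 4 has no place for the Other eSAE class that SAP 4.3.1.4 says is presented.

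**The case against.** The strongest reply is that 10.6 conflicts in wording but loses nothing. Its express waiver concerns health authorities, and the missing sponsor report is only inferred from the phrase that limits the duty to that case. Section 10.1 makes any HCP form a trigger, without exception. SAP 4.3.1.4 plans to show exactly these rejected cases and excludes no organ class. Exempting endpoint events from SAE reporting is a deliberate design, and an independent data monitoring committee sees unblinded safety data.

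Much of this stands, and it defeats three stronger readings that a reader might take from 10.6:

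- *Rejected cases never reach the sponsor.* The documents do not support this. The general rule still requires the report, and no text says that 10.6 overrides it.
- *Other eSAE contains no cardiovascular or respiratory events by construction.* SAP 4.3.1.4 states no such exclusion.
- *No other safety stream sees the event.* Only the twice-monthly table excludes it expressly. SAP 3.2 collects SAEs resulting in hospitalization from the registers for 6 months, and SAP 5.7 plans a hospitalization analysis without stating an endpoint exclusion. What may be lost is the suspicion, not the event.

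The endpoint window also matters. The primary endpoint starts 14 days after vaccination, so on a strict reading the waiver does not reach days 0 to 13, when an acute reaction is most naturally suspected. However, neither 10.6, footnote b nor the 10.1 exclusion states a time limit of its own.

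The reply does not remove the contradiction. Its own argument is that the general rule should govern, and 10.6 does not say that.

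**Conclusion.** The conflict holds for a narrow class: non-fatal endpoint hospitalizations that an HCP suspects and the investigator considers unrelated. For these, 10.6 with footnote b and the general rule in 9.2.2.1, 9.2.2.3.2 and 10.1 cannot both be followed. Capture in the eSAE data and review by the sponsor are therefore uncertain, not absent.

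The number affected cannot be derived from the documents. The illustration above suggests a few cases at most in the season that was run, and it rests on assumed rates.

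A reader might also infer that the effectiveness result is compromised. It is not: the rVE estimate depends on register hospitalizations and vaccine group only. The effect is confined to the SAR and Other eSAE tables, the sponsor's second causality opinion and expedited reporting. The wording should still be corrected, because a rule that can drop a suspected reaction contradicts the plan's own principle, and correcting it costs very little.

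**What to change.** **Protocol 10.6.** Reword the exception so that it follows the general rule: an endpoint event that the reporting HCP or the Principal Investigator suspects to be related to the study vaccine is entered in the SAE eCRF within 24 hours of first awareness by THL study personnel, whatever the investigator's own assessment. Make footnote b in 9.2.2.1 subject to the same exception. The Synopsis has no investigator filter to replace; it needs only to say who defines an endpoint-related SAR. This is one sentence plus alignment, and a handful of extra eCRFs. Because enrollment has ended, it matters mainly if the text is used again.

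**For the study as run.** The HCP forms are source data under Protocol 13.2, so the gap can be measured:

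1. Reconcile every SAR/AESI paper form against the eSAE panel.
2. List any form for an endpoint-coded event that has no eCRF, by vaccine group after unblinding.
3. State in the CSR which rule was applied.

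**SAP.** Align the SAR definition in 4.3.1.5 with Protocol 9.2.2.1, or label it as the investigator-related subset. Add the Other eSAE class to the panel description in section 4.

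The cost is a check of the paper forms and a few lines of text. The endpoint analysis does not change.

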## 11 Data Collection and Management

### 11.1 Data Collection

At enrollment, the data related to Visit 1 will be collected by qualified HS nurses and documented in the ICF (refer to [Section 5.2.2](#)). The original ICFs will be sent to the THL on a regular basis (ie, preferably weekly and at least every month) for data entry.

The suspected SARs, fatal SAEs, and AESIs will be individually collected electronically by the Principal Investigator or authorized designee using the SAE eCRF in the EDC system. This form has been designed specifically for this study under the responsibility of the Sponsor, using a validated Electronic Records / Electronic Signature-compliant platform (21 CFR Part 11).

To ensure the correct and consistent completion of the SAE eCRF, the Sponsor or authorized representative will provide all necessary tools, instructions, and training to the Principal Investigator and designated THL staff involved in data entry prior to study start. Additional instructional documents such as training manuals and completion instructions will be provided to assist with data entry during the course of the study.

Upon completion of training, each user requiring access to the EDC system will be issued a unique username and password. In the event of a change in study personnel, each newly assigned individual will receive a unique username and password; the username and password of a previous user may not be reissued. If any study personnel leave the study, the Principal Investigator is responsible for informing the Sponsor immediately so that their access is deactivated. An audit trail will be initiated in the EDC system at the time of the first data entry to track all modifications and ensure database integrity.

The Principal Investigator or delegate sub-Investigator is responsible for the timeliness, completeness, and accuracy of the information in the SAE eCRF; must provide explanations for all missing information; and must sign the form using an e-signature.

In addition to the safety data collected, data in the national health registers will be collected at THL through linkage of registers using the Finnish PIC.

These data will include prospective and retrospective data for the subjects, but may also include collection of aggregated data from individuals not enrolled in the study to be used in the study safety evaluation as baseline data for signal detection regarding non-fatal SAEs.

[Table 11.1](#) describes the different Finnish health registers that will be used to collect data for this study.

**Table 11.1: List and description of the Finnish health registers**

Digital and Population Data Services Agency (DVV), previously Population Register Centre	
The Finnish Population Information System, maintained by the Digital and Population Data Services Agency (DVV), is a computerized national register that contains exact enumeration and basic information about Finnish citizens and foreign citizens residing permanently in Finland (44). Data will be used for retrieving the address of the study source population to send invitation letters by mail. Additionally, data from population information system will be used for the follow-up of the vital status with minimal delays. Demographic data can be collected through DVV.

National Care Registers (HILMO and AVOHILMO)	
The Care Register for Health Care (HILMO), a hospital discharge register maintained by THL (previously known as STAKES) since 1994, will be used for identification of hospital visits, inpatient hospitalizations, and the occurrence of complications and resource use (45). The HILMO contains all outpatient and inpatient diagnoses (ICD-10) for patients who received care at the Finnish hospitals. The discharge notifications include the personal identification data (including PIC), site of treatment, medical specialty code, admission and discharge dates, ICD-10 codes, type of admission (emergency/schedule/transfer). The data are collected locally on an ongoing basis, but transfers to the national register are in batches. The process of data collection may be expedited with monthly or even more frequent data collection. The data for this study will be collected monthly.
 
The Register of Primary Health Care Visits (AVOHILMO) contains data on outpatient primary health care visits in public health care centers (46). The data collection includes all public outpatient primary health care delivered in Finland since 2011. Private outpatient clinics are not covered at the moment. The data dispatch from the health care centers is scheduled to occur every night.
 
The national vaccination register is part of the Avohilmo register. Data on all vaccinations administered at the public HCC/HS are sent overnight to THL.

Social welfare (THL Care register for Social Welfare)	THL Care register for Social Welfare contains data on nursing home admissions, supported accommodation services, and home care customer status annually on 30 November. These data cannot be obtained in the study database as directly identifiable linked individual-based data, but aggregate data only. The data linkage will be performed centrally at the THL Department of Information Services. The feasibility of social welfare data to be used in the study will be explored.

National Infectious Disease Register (NIDR)	
Data from the National Infectious Disease Register (NIDR), maintained by KTL/THL since 1995 can be used for identifying laboratory-confirmed influenza cases. There has been a recent increase in the number of reported influenza cases due to increased testing (access, media attention) and reporting. Additionally, NIDR can be used for identification of secondary infections, like laboratory-confirmed invasive bacterial disease (Escherichia coli, Staphylococcus aureus and Klebsiella species being the most common findings).
 
The NIDR is a population-based and laboratory-based surveillance system (47) (48). All Finnish clinical microbiology laboratories are required to notify detections of influenza (either by culture, serology, antigen detection, or polymerase chain reaction [PCR]). Each notification includes the date and type of specimen, microbe detection method, date of birth, sex, and place of sample obtaining. Duplicate reports of cases within 3 months are merged into episodes at THL. Cases are generally recorded into the NIDR database within 2 weeks of the date of sample collection. The PIC is available for linkage of the cases in the NIDR since 2004.
 
There is also sentinel surveillance for influenza in selected outpatient clinics and in the hospital intensive care units. Respiratory tract samples are requested to be sent to THL based on a specified sampling frame. These are analyzed by real-time PCR which detects various influenza subtypes and lineages. Additional analyses may include sensitivity to antiviral drugs and genetic and antigenic changes.

Statistics Finland	The cause of death register is controlled by the Statistics Finland (49).
Social Insurance Institution registers (KELA)	
The Social Insurance Institution (KELA) benefits register may be used for evaluation of baseline comorbidity, resource use related to complications of influenza and to the use of medications as explorative endpoints (50).
 
KELA register has been operational since 1964 with multiple changes and adaptations to current Finnish laws. Expanding data has been collected on national insurance reimbursements including drug prescriptions since 1995. Currently, the register includes data on reimbursable medications only, and therefore, the register may not be complete for all prescribed medications. Delay for data collection purposes is minimum 4 months. Special reimbursement decision can be used for identification of chronic diseases like diabetes, heart disease, lung disease, etc.
 
KELA collects also data on disability benefits and services that might be relevant for long-term cost evaluation. Changes in the Care allowance for pensioners will be collected (before and after the influenza season).
 
The Prescription Centre of the Social Insurance Institution (KELA) has the e-prescription data since its introduction in 2010. The data collection has been nationwide since 2017.

